### Objective of the study

The overall objective of the Exo4Work project is to design, develop and validate a smart modular exoskeleton for spinal, torso and upper limb support to assist workers, to reduce the physical load on workers, keep older workers active for a longer period of time, increase quality of work, reduce fatigue, and prevent injuries.

The objective of this study is to assess physical and mental load of industrial work in laboratory conditions.

### Introduction

It is acknowledged that industrial workers face high risks of musculoskeletal injuries, such as lower back pain, since they work in small places and non-ergonomical postures. Besides providing preventive evidence-based practical guidelines to support occupational safety and health, a potential solution can be found in the research field of Human-Centered Robotics, i.e. the implementation of exoskeletons. An exoskeleton is a wearable, external mechanical structure that assists the operator during human movement.

Companies gain increasing interest in the implementation of exoskeletons in the working environment with the aim to improve work efficiency and reduce work-related injuries. The research field about the implementation of exoskeletons in field conditions is novel. After an observational, ergonomic evaluation of work postures during different industrial tasks in an earlier stage of the project, the current study will simulate industrial work in laboratory settings. The outcome will be an ergonomic evaluation of postures of industrial work using physiological and biomechanical data.

### Study design

The design of the study is interventional, cross-over (in laboratory conditions).

### The subjects

*Number of subjects*

During this experiment twelve healthy subjects will be recruited. Experiments wherein industrial work will be simulated in laboratory settings will be conducted. These experimental trials will take place at VUB (climate chamber, research group MFYS).

#### *Inclusion criteria*

Healthy males between 18-65 yrs

#### *Exclusion criteria*

Injuries

#### *Replacement of subjects*

New subjects will be recruited in case of drop out.

#### *Restrictions and prohibitions for the subjects*

/

#### Procedures

[figure not shown]
The physical and mental load of simulated industrial work will be investigated in laboratory conditions. Each subject will perform a pre-test and three lab trials. The pre-test (1h) will include basic biometric measurements, simple motor tasks (e.g. squatting), a dual-task walking task using the cognitive Stroop task to determine reaction time and accuracy during walking (Arcelin et al., 1998) and a familiarization trial of the simulated industrial task (described further down this protocol).

A first lab trial will include a cognitive task (90 min, 2-back task (Massar et al., 2010) (cognitive component). During a second trial a 90 minute walking task will be performed (physical component). The third trial will consist of a simulated industrial task (physical and cognitive component). The simulated industrial task will be a 90 minute task during which boxes (max 15 kg) will be moved from one place to another (0.05 Hz) while also performing a cognitive task (2-back task). Before and after the cognitive, physical or simulated industrial task a 10 minute Stroop task will be performed.

In the laboratory the ergospirometric device K5 (Cosmed) will be attached to the subject to measure oxygen consumption (via a mask) and indirectly energy expenditure. A heart frequency monitor (Polar) will be attached using a chest belt. The non-invasive electro-encephalography (EEG) and electro-myography (EMG) electrodes will be placed on the subjects head using non-invasive EEGcap and EMG surface electrodes, respectively. Furthermore, different questionnaires will be used, i.e. the Rating of Perceived Exertion (RPE), the Profile of Mood States (POMS), the Local Discomfort Scale, the Visual Analogue Scale (VAS) for fatigue, Nasa TLX, heat scores and Need for Recovery scale. In simulated industrial settings oxygen consumption and heart rates will be determined, as well as following questionnaires: RPE, POMS, Local Discomfort Scale, VAS for fatigue, Nasa TLX, heat scores and Need for Recovery scale.

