#### Flowchart

Twelve subjects will be included to conduct experiments in laboratory conditions. Three experimental trials per subject will be planned. One trial will include a simulated industrial task during which boxes are moved while walking on a treadmill. The intensity of the task will be determined based on the results of an ongoing observational study which ergonomically evaluates industrial work (approximated max 15 kg, lifting frequency of 0.05 Hz). During the second trial, a 90 minute normal walking task on a treadmill will be executed. The third trial will include a 90 minute cognitive task (2-back task). Before and after each trial a 10 minute Stroop task will be performed in order to analyse the cognitive performance of the subject. The total duration of one experimental trial is 3 hours.

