#### *Statistical analysis*

The physiological data will be statistically analysed with IBM SPSS statistics 25. Normality tests (Shapiro-Wilk normality testing) will precede parametric or non-parametric testing. Data

analysis of electro-physiological data will be conducted using Brain Vision Analyzer, wherein data will be pre-processed (signal filtering, re-referencing, artefact removal) and processed (power spectral analysis, coherence and non-invasive brain imaging). From Brain Vision Analyzer files will be extracted and inserted in standardized Low Resolution Brain Electromagnetic Tomography or sLORETA. The statistical analysis performed in sLORETA is Statistical non-parametric mapping or SnPM using the Fisher's permutation test that relies on a Bootstrap method with 5000 randomizations. [name] ([[contact]](mailto:[contact])) is responsible for the physiological data analyses.

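### Does the Stroop comparison need a trial without a task, or a written contrast, before the mental load of the industrial task can be assessed?

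*Combined protocol and SAP*

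**What the plan says.** Under Objective of the study the aim is stated as: "The objective of this study is to assess physical and mental load of industrial work in laboratory conditions". Under Study design: "The design of the study is interventional, cross-over (in laboratory conditions". Randomisation/blinding adds that trial order is random, to guard against sequence effects.

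Under Procedures, "Each subject will perform a pre-test and three lab trials". One trial is a 90-minute 2-back task, labelled as the cognitive component. One is 90 minutes of walking, labelled as the physical component. One is the simulated industrial task, labelled as both. Flowchart adds "One trial will include a simulated industrial task during which boxes are moved while walking on a treadmill" and "During the second trial, a 90 minute normal walking task on a treadmill will be executed".

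Procedures places the Stroop task as follows: "Before and after the cognitive, physical or simulated industrial task a 10 minute Stroop task will be performed". Flowchart gives its purpose: "Before and after each trial a 10 minute Stroop task will be performed in order to analyse the cognitive performance of the subject".

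Statistical analysis says "The physiological data will be statistically analysed with IBM SPSS statistics 25", preceded by Shapiro-Wilk tests that lead to unnamed parametric or non-parametric tests. The rest of that section concerns the electrophysiological data. It contains no rule for Stroop.

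**The concern.** Stroop is the only cognitive performance measure that the text places in all three trials, since the walking trial has no 2-back. Two analyses can be imagined. One tests the before-after change within the industrial trial; the other compares that change between trials. They estimate different quantities and could differ in sign.

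The within-trial change carries everything that would shift between the two Stroop sessions without the task. Practice could hide a real load, and elapsed time could look like one. Randomising trial order does not help here, because the second Stroop session follows the first in every order. More subjects do not help either, because this is bias and not imprecision. The between-trial comparison avoids the problem but never isolates the effect of the whole industrial task. If a report presented the industrial trial's own Stroop change as its mental load, that figure would be off by the full time-and-repetition effect.

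**Working it through.** **Inputs.** Three trials, their contents and the Stroop timing come from Procedures and Flowchart; 12 subjects from Sample size calculation; 3 h per trial from Flowchart; the 1 h pre-test from Procedures. The documents give no Stroop effect, standard deviation, alpha or power. The plan's 12 was set by similarity to an earlier study, so there is no calculated figure to reproduce.

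**What the three trials identify.** Write the expected Stroop change (after minus before) in terms of time and repetition T, walking W, box moving B and 2-back K:

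- cognitive trial: T + K
- walking trial: T + W
- industrial trial: T + W + B + K

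That is three equations in four unknowns (rank 3). If T is equal across trials, the differences are:

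- industrial minus walking = B + K, provided the walking demand is the same in both
- industrial minus cognitive = W + B, provided the 2-back is the same in both
- cognitive minus walking = K - W, which is the first difference minus the second and adds nothing new

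The whole task is W + B + K. A combination a(cognitive) + b(walking) + c(industrial) has coefficients (a+b+c, b+c, c, a+c) on (T, W, B, K). Setting those on W, B and K to 1 forces c = 1 and a = b = 0. The coefficient on T is then 1, not 0, so the whole task is not estimable. An interaction term in the industrial trial does not alter this. A task-free trial (T alone) would give rank 4, and industrial minus task-free would then be the whole-task effect, including any interaction.

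**Illustration with assumed values.** Let X be whatever the industrial task adds beyond the 2-back effect C and the walking effect P. In ms, (T, C, P, X) = (0, 20, 10, 10) and (40, -20, -30, 50) both give mean changes of 20, 10 and 40 in the cognitive, walking and industrial trials. The whole-task effects C + P + X are 40 and 0.

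**Size of the within-trial distortion.** With L the whole-task effect, the industrial trial's own change has expectation L + T, so its ratio to L is 1 + T/L. For assumed T/L of -1, -0.5, 0, 0.5 and 1 the ratio is 0%, 50%, 100%, 150% and 200%. This range restates the assumption. Nothing in the documents says where T/L lies.

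**Precision of the between-trial comparison.** For a paired t test with n = 12, df = 11, two-sided 5% and 80% power, the noncentral t gives a detectable difference of 0.889 SD of the paired difference. Multiplying by sqrt(2(1 - rho)) expresses it in SDs of a single-trial change, with rho assumed:

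| rho | detectable difference |
|---|---|
| 0 | 1.257 |
| 0.3 | 1.051 |
| 0.5 | 0.889 |
| 0.7 | 0.688 |

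If two contrasts were each tested at 2.5%, 0.889 would become 1.01. These figures concern precision and say nothing about the size of the alleged bias.

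**Cost of a task-free trial.** 12 x 3 h = 36 h of laboratory time. Each subject goes from 1 + 3 x 3 = 10 h to 13 h, with one more visit at which to drop out.

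**Does the text leave the comparison open?** The study is declared a cross-over, the order is randomised against sequence effects, and the trials are labelled cognitive, physical, and both. Each of these features serves comparison between trials. The stated purpose of the Stroop is cognitive performance, with no mention of a whole-task effect. The Introduction describes the study's outcome as an ergonomic evaluation from physiological and biomechanical data, which does not include Stroop.

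**The case for a change.** The strongest argument for a change is that the remedy is nearly free. One paragraph could define the Stroop outcome as after minus before, test its difference between trials with trial and period as fixed effects and subject as random effect, and keep the within-trial change descriptive. A before-and-after measurement does invite a within-trial test, and nothing in Statistical analysis forbids one. The pre-test Stroop is performed while walking, so it cannot serve as a task-free control. All of this stands.

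It does not make the plan wrong. That paragraph would record the analysis that the design already implies, and its two contrasts are the same two sums that the concern counts as a shortcoming. The walking and 2-back trials are sound active controls for statements about added load. The repetition argument is also weaker than a count of six Stroop sessions suggests. A within-trial change spans one repeat, practice across visits is a period effect that random order addresses, and the pre-test already gives some exposure to the task.

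**Conclusion.** No change to the plan follows. Without a task-free trial, Stroop cannot give the effect of the industrial task as a whole, and the within-trial change cannot be separated from time and repetition. But the plan promises neither reading, and its design points to between-trial comparison. The missing Stroop rule is a gap in detail that analysts of a three-period cross-over would fill sensibly. The general load of the task is described by oxygen consumption, heart rate, RPE and NASA TLX, which the point does not touch.

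The 0% to 200% distortion rests wholly on assumed values of T and L, and would arise only if a within-trial change were reported as load. A task-free trial would cost 36 laboratory hours and an extra visit for every subject, and its merit is open to debate.

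The conclusion assumes that the time-and-repetition effect is similar across trials, and that walking demand and the 2-back match where the contrasts need them. The Procedures figure is not available and may bear on the matching, but the text consistently gives three trials. If a report did present the industrial trial's own Stroop change as its mental load, the objection would apply to that report.

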#### Flowchart

Twelve subjects will be included to conduct experiments in laboratory conditions. Three experimental trials per subject will be planned. One trial will include a simulated industrial task during which boxes are moved while walking on a treadmill. The intensity of the task will be determined based on the results of an ongoing observational study which ergonomically evaluates industrial work (approximated max 15 kg, lifting frequency of 0.05 Hz). During the second trial, a 90 minute normal walking task on a treadmill will be executed. The third trial will include a 90 minute cognitive task (2-back task). Before and after each trial a 10 minute Stroop task will be performed in order to analyse the cognitive performance of the subject. The total duration of one experimental trial is 3 hours.

### Randomisation/blinding

The order of the executed trials will be randomly assigned to avoid possible sequence effects. No blinding occurs.

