### Study analysis

#### *Sample size calculation*

Twelve subjects will be recruited to perform laboratory tests in a cross-over design. This amount of subjects is similar to the cohort size used in an earlier cross-over mental fatigue study concerning exercise (Martin et al., 2015).

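### Random order alone does not protect the industrial-task contrasts from unequal carry-over, and no interval or like-for-like visit conditions are stated

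*Combined protocol and SAP*

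**What the plan says.** The Study design section reads "The design of the study is interventional, cross-over (in laboratory conditions", and the Procedures section adds "Each subject will perform a pre-test and three lab trials". The three tasks are a 90-minute 2-back, 90 minutes of walking, and 90 minutes of box moving combined with a 2-back. The last is described as follows: "The third trial will consist of a simulated industrial task (physical and cognitive component". The ordinal there is a label, not a position, because the Flowchart section lists the tasks in a different sequence and the order is randomised.

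The only stated protection against order problems is in Randomisation/blinding: "The order of the executed trials will be randomly assigned to avoid possible sequence effects". No balanced set of orders is named. The Flowchart section says "Three experimental trials per subject will be planned" and gives 3 hours as the length of one trial, but no spacing between trials. The section headed "Restrictions and prohibitions for the subjects" contains only a slash. The Par-Q is stated for the time before the first trial, and no recovery check is stated before the second or third. A 10-minute Stroop task is planned before and after every task.

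The Statistical analysis section names a normality test followed by parametric or non-parametric testing, with no period, sequence or carry-over term. On size it says "Twelve subjects will be recruited to perform laboratory tests in a cross-over design" and justifies this only by precedent: "This amount of subjects is similar to the cohort size used in an earlier cross-over mental fatigue study concerning exercise".

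**The concern.** Randomising the order spreads period effects such as learning or habituation evenly over the tasks on average. Carry-over is different, because it depends on which task came before. If one task leaves more behind than the others, its residue falls only on the other tasks and never on itself, and the contrasts shift however the orders are drawn.

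Unequal carry-over is plausible here. The industrial task is the only one with both a physical and a cognitive load. At 0.05 Hz for 90 minutes it comes to 0.05 × 5,400 s = 270 box moves, if one box is moved per cycle. Several outcomes could respond to residual fatigue: VAS fatigue, POMS, local discomfort, need for recovery, Stroop performance, heart rate and EEG. The industrial contrasts matter most for the study's objective, the load of industrial work.

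A second, separate cost comes from the empty restrictions entry. A subject may arrive rested at one visit and tired, exercised or caffeinated at another. Even with no carry-over between trials, that adds within-subject noise to a comparison of 12 people.

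**Working it through.** **Plan figures to reproduce.** There are none. The sample size of 12 has no effect size, SD, alpha or power behind it, and no carry-over size is given. What follows is algebra on the stated design plus illustrations with declared assumptions.

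**Inputs from the plan.** Three tasks, industrial (I), walking (W) and cognitive (C); three periods; 12 subjects; random order.

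**Step 1: bias with balanced orders.** Let τ be a task's direct effect and λ the amount it leaves in the next trial. The six orders are CWI, CIW, WCI, WIC, ICW and IWC. Each ordered pair of neighbours occurs in 2 of the 6 orders, so each task directly follows each other task in one third of subjects. Apart from effects common to all tasks:

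- mean under I = τ_I + (λ_W + λ_C)/3
- mean under W = τ_W + (λ_I + λ_C)/3
- I − W = (τ_I − τ_W) + (λ_W − λ_I)/3

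Likewise I − C is shifted by (λ_C − λ_I)/3 and W − C by (λ_C − λ_W)/3. So:

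- Equal carry-over from all tasks gives no bias in any contrast.
- Carry-over L from the industrial task only gives −L/3 in I − W and I − C, and 0 in W − C.
- Carry-over from W and C at half that of I gives −L/6 in the two industrial contrasts and 0 in W − C.

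A least-squares fit gives the same values with or without period terms. Adjusting for period therefore does not remove this bias.

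**Step 2: illustration of size.** Assume direct effects of 1.0 (I) and 0.4 (W and C), with a fraction f of the previous task's effect remaining at the next trial. The true I − W contrast is 1.0 − 0.4 = 0.60, and the bias is (0.4f − 1.0f)/3 = −0.2f.

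| f | bias | observed contrast | relative change |
|---|---|---|---|
| 10% | −0.02 | 0.58 | −3% |
| 25% | −0.05 | 0.55 | −8% |
| 50% | −0.10 | 0.50 | −17% |

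I − C gives the same values, and W − C is unbiased.

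**Step 3: how the orders are drawn.** If each subject's order is drawn independently, the chance of exactly two subjects per order is 12!/(2^6 × 6^12) = 0.3%. At f = 50%, simulating such draws gives a mean bias of −0.10 in I − W. The 95% range is −0.25 to +0.04 for the unadjusted contrast and roughly −0.18 to −0.02 with period in the model. Balanced orders remove this spread but not the mean. A single cyclic Latin square (CWI, WIC, ICW) would not do: with carry-over L from the industrial task only, it puts −2L/3 into I − C and W − C and 0 into I − W.

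**Step 4: noise from unlike arrival conditions.** Assume a paired t-test, two-sided alpha 0.05, n = 12. The standardised paired difference giving 80% power is 0.89. If the SD grows by a factor k, that difference becomes 0.89/k and the effective sample size 12/k².

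| k | standardised difference | power | equivalent n |
|---|---|---|---|
| 1.00 | 0.89 | 80% | 12 |
| 1.10 | 0.81 | 72% | 9.9 |
| 1.25 | 0.71 | 61% | 7.7 |

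The value 0.89 is only the reference point for 80% power. Neither it nor the inflation factors come from the plan.

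**The case against.** A reader might infer that the trials run back to back. The documents do not say so: spacing is unstated, not zero, and the Procedures section contains a figure that is not shown and may hold a schedule. The restrictions entry is text and does not depend on that figure.

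A reader might also infer that the results will be biased. That does not follow. Bias needs fatigue that outlasts the interval and differs by task, and the documents give no figure for either. With well-spaced visits, 50% residual is an extreme case, and at 10% to 25% the illustrated bias is only 3% to 8% of the contrast. Nor are all contrasts affected: with balanced orders, walking versus cognitive is untouched by industrial carry-over. The direction towards no difference holds on average or under balance, not for every random draw. Calling the industrial task the heaviest is an inference from its double load; the Flowchart section leaves its intensity to be set from an ongoing study.

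The Stroop task before each task is a real partial safeguard. A change score cancels any carry-over that acts equally on the values before and after. However, the plan does not commit to change scores, and it states no pre-task baseline for the questionnaires, heart rate or oxygen uptake.

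These points limit the claim but do not remove it. Random order is still credited with something it cannot do, and nothing in the readable text makes a subject's three visits comparable.

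**Conclusion.** The point holds in conditional form. If carry-over lasts to the next visit and is larger after the industrial task, the two industrial contrasts can be biased by about one third of the carry-over difference. That one-third factor follows from the design under balanced orders and first-order carry-over. The size of the carry-over is unknown, so the 3%, 8% and 17% reductions are illustrations resting on assumed effects of 1.0 and 0.4. The power losses likewise rest on an assumed alpha, effect and SD inflation. The documents do not establish that bias will occur.

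The firmest part is the empty restrictions entry: as written, nothing keeps a subject's visits alike in a 12-subject within-subject comparison of state-dependent outcomes. The change should be made before data collection, because unlogged arrival conditions and unequal spacing are hard to repair afterwards. Confidence is medium.

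**What to change.** - **Restrictions section.** Replace the slash with a requirement that each subject's three visits take place under like conditions: the same time of day and the same pre-visit conditions, logged on arrival. Require one minimum interval between trials for all subjects. The length of the interval and the content of the conditions are for the investigators to set. If the Procedures figure already holds a schedule, repeat it in the text.
- **Randomisation/blinding section.** Allocate all six orders in balance, two subjects per order, and let a replacement subject take over the order of the one who dropped out. Reword the claim that random order avoids sequence effects.
- **Statistical analysis section.** Include period in the model. Analyse Stroop with each visit's pre-task value as baseline, and do the same for VAS fatigue and POMS if they are taken before the task.
- **Reporting.** Show pre-task values by preceding task descriptively. With 12 subjects and two transitions each, a non-significant carry-over test would not show that carry-over is absent, so no such test should decide the analysis.

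The cost is protocol wording, a short arrival log and slightly harder scheduling. No extra visits or subjects are needed.
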